COVID-19 incidence, particularly among underserved minority and rural Oklahomans. Oklahoman's are also reporting SARS-CoV-2 vaccine hesitancy and signs of slowing vaccine uptake, with increased hesitancy among American Indian and rural populations. The project aims to work with ongoing community testing events to implement interventions to improve vaccine uptake among Oklahoma's underserved populations.

I. Statistical Methods

Aim 1 Analysis. Digitally recorded focus groups will be securely uploaded to protected servers and transcribed using NVivo Transcription. Transcriptions will be team coded for conceptual themes using QSR NUDIST Vivo12 Pro for Windows.¹⁶ Investigators will develop a code book. Throughout the coding process, qualitative data will be categorized, connections made between categories, and core categories identified and systematically linked to other categories. Focus group data will inform intervention selection and needed modifications for community acceptability/relevance.

Aim 2 Analysis. All analyses are intent-to-treat. Outcome measures will be assessed at baseline, 30 days, and 60 days follow-up. At the outset, we will examine the frequency distributions of all variables. We will compare the baseline characteristics to assess whether randomization distributed covariates evenly. We will determine whether there is differential dropout and consider developing probability-of-completion weights to obtain unbiased estimates of treatment effect.

The primary analysis will assess the effects of each intervention component in terms of its association with the primary outcome (intent to receive a COVID-19 vaccine immediately after the interventions are completed). Cross-sectional analyses will be conducted for outcomes assessed at 30 and 60 days. For binary outcomes, chi-square tests will be used to compare the outcomes between groups. For continuous outcomes, two-sample t-tests or Wilcoxon rank sum tests, whichever is more appropriate, will be used to compare between groups. A longitudinal analysis using Generalized Estimating Equations (GEE) techniques will also assess the overall impact of the intervention by including data from all follow-up time points.

As a secondary analysis, we will compare vaccine coverage among counties with an intervention compared to counties without intervention to see whether coverage increased in the study counties using a chi-square test. We will use publicly available data from the Oklahoma State Department of Health and/or Centers for Disease Control and Prevention for this analysis.

Sample size and power calculations. Power calculations are based on our primary analysis, which is to assess the effect of each intervention component on increased intention to receive a COVID-19 vaccine immediately after the intervention. This is a two-sample comparison between participants that receive one intervention component and those that receive the control. Our pilot implementation will include a single site with an estimated 500 participants.

Our outcome of interest is also assessed at 30 and 60 days follow-up to measure intention to receive a COVID-19 vaccine, which allows us to use a longitudinal generalized estimating equations approach wherein power is proportional to the within-site

correlation. Using PASS v16, we assume the intra-cluster correlation within each site is 0.01. Our power analysis is based on data from both pilot and full implementation of the study results. Assuming a minimum n=167 participants per site for a minimum of sites, a Type 1 error rate of 0.05, and an estimated standard deviation of 5, we have over 80% power to detect a mean difference of 20.

Data and Safety Monitoring Plan

Drs. [name] and [name] assure that oral informed consent is obtained prior to conducting the focus groups (Aim 1) and written informed consent and HIPAA authorization are obtained for the intervention (Aim 2) prior to performing any research procedures, that all subjects meet eligibility criteria, and that the study is conducted according to the IRB-approved research plan.

Study data are accessible at all times for the PI/PD to review. [name] will review the study conduct weekly and the PI/PD will review the study conduct on a monthly basis. Study conduct will include accrual, drop-outs, and protocol deviations. The PI/PD will review adverse events individually in real-time and in aggregate on a weekly basis.

COLLECTION AND REPORTING OF SAEs AND AEs

For this study, the following standard AE definitions are used:

Adverse event: Any unfavorable and unintended sign (including an abnormal laboratory finding), symptom or disease temporally associated with the use of a medical treatment or procedure, regardless of whether it is considered related to the medical treatment or procedure.

Serious Adverse Event: Any AE that results in any of the following outcomes:

- Death
- Life-threatening
- Event requiring inpatient hospitalization or prolongation of existing hospitalization
- Persistent or significant disability/incapacity

AEs are graded according to the following scale:

Mild: An experience that is transient, & requires no special treatment or intervention. The experience does not generally interfere with usual daily activities. This includes transient laboratory test alterations.

Moderate: An experience that is alleviated with simple therapeutic treatments. The experience impacts usual daily activities. Includes laboratory test alterations indicating injury, but without long-term risk.

Severe: An experience that requires therapeutic intervention. The experience interrupts usual daily activities. If hospitalization (or prolongation of hospitalization) is required for treatment it becomes an SAE.

The study uses the following AE attribution scale:

Not related: The AE is clearly not related to the study procedures (i.e., another cause of the event is most plausible and/or a clinically plausible temporal sequence is inconsistent with the onset of the event).

Possibly related: An event that follows a reasonable temporal sequence from the initiation of study procedures, but that could readily have been produced by a number of other factors.

Related: The AE is clearly related to the study procedures.

AEs are identified by the study coordinator during weekly visits or by phone call throughout the study duration, and AEs will be assessed at time of study follow-up visits. SAEs and specific procedure-associated AEs are reported to the PDs within 24 hours. In addition, all AEs are reported according to the University of Oklahoma Health Sciences Center Institutional Review Board AE reporting guidelines.

MANAGEMENT OF RISKS TO SUBJECTS

Expected AEs

There are no expected AEs as a result of this study, as the intervention components will be standard and evidence-based strategies and non-therapeutic. Potential interventions strategies are educational in nature with a minimal risk finger stick for serology tests and are not anticipated to have AEs.

Expected SAEs

There are no expected SAEs as a result of this study, as the intervention components will be standard and evidence-based methods, primarily educational in nature with a minimal risk finger stick for serology tests.

AE and SAE Management

The research coordinator will monitor outcomes and make adjustments to the protocol if unanticipated problems arise.

J. Data Sharing

Sharing of primary epidemiological data that is generated as part of this project will occur as allowed by the University of Oklahoma Health Sciences Center IRB.

Aggregate data will be submitted to clinicaltrials.gov as required by NIH.

Identifiable data will be uploaded, with participant consent, to the RADx-UP data repository as required by the NIH grant terms and conditions. A data transfer agreement will be fully executed prior to sharing data with NIH. If participants decline to share their identifiers, including all identifiable information or zip code with the Duke Clinical Research Institute, only de-identified information will be shared for these participants.

Specifically, only aggregate data that cannot be linked back to individual people will be shared upon request in accordance with IRB. We will adhere to NIH Policy on sharing

biomedical research resources. We will make de-identified data available for users under a data-sharing agreement that requires the user to (1) agree to use the data for research purposes only; (2) have a plan in place to secure the data using appropriate computer technology; and (3) agree to destroy or return the data after analyses are completed.

K. Confidentiality

No one will have access to the data files and servers except the investigators. All data will be stored on Redcap or an OUHSC secured drive behind a firewall that requires a log-in and password. When the drive is not in use, the user will log off. The server is stored in a locked location. To transfer de-identified, aggregate data between OU Norman and OUHSC for development of research products (i.e., posters, manuscripts, dissertation), we will use a secure file transfer system/method. This will help safeguard the confidentiality and integrity of sensitive data in compliance with HIPAA and other regulatory requirements. We will encrypt the data prior to sending through the secure file transfer system. Published reports and presentations will not include any individually identifiable data and only aggregate statistics will be reported.

L. Literature Cited

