Overall Study Design: Interventions will address three primary areas to improve vaccination uptake: (1) process (text messages); (2) teachable moment messaging (motivational interviewing); and (3) barrier elicitation and reduction (electronic survey with tailored questions/prompts). In our selection of potential interventions, we will use the Community Preventive Services Task Force (CPSTF)⁹ and the NIH Behavior and Social Sciences Research-Coordinating Committee Rapid Working Group on COVID-19 Vaccine Communication guide, among other resources.¹⁰ We will work with the NIH RADxSM-UP Coordination and Data Collection Center (CDCC) to ensure collection of Common Data Elements.

Table 2. Experimental conditions in the 2³ factorial design for the COVID-19 vaccine intervention

Condition	Factor		
	Process Improvement	Teachable Moment Messaging	Barrier Elicitation and Reduction
1	No	No	No
2	No	No	Yes
3	No	Yes	No
4	No	Yes	Yes
5	Yes	Yes	Yes
6	Yes	Yes	No
7	Yes	No	No
8	Yes	No	Yes

Outcome metrics characterizing SARS-CoV-2 vaccine uptake. Our **primary outcome** will be intention to receive a COVID-19 vaccine post-intervention. We will measure this with the question “How likely are you to get an approved COVID-19 vaccine?” and “If you have received 1 dose of the Janssen vaccine or 2 doses of the Moderna or Pfizer vaccine, how likely are you to get an approved booster shot?” We will compare intention to receive a COVID-19 vaccine or booster among those receiving the interventions compared to those not receiving the intervention (see details on analysis below).

Our **secondary outcome** will be vaccine uptake, including self-report of receiving an initial dose of any approved vaccine, two doses of Pfizer or Moderna vaccines, or a booster of any approved vaccine. We will request the manufacturer of the vaccine and the approximate dates the vaccine was received from the participant.

Aim 2.1. Pilot Implementation.

Study Design. Participants at the pilot sites will be randomized to receive a text message and/or education message (detailed below) delivered through a tablet or no intervention. We will also conduct a pilot of motivational interviewing messages that are tailored based on antibody test results (or lack of testing if the participant declines an antibody test).

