We will collect a survey using Research Electronic Data Capture (REDCap) software (Nashville, TN) to allow for descriptive statistics, assessment of study outcomes, and ensure the randomization is balanced regarding these characteristics.

Intervention Procedure

1. Screening Form to identify eligibility for the study. This will include age, ability to read and speak English, vaccine status and dose information (see eligibility criteria), and having symptoms of COVID-19 or positive test for COVID-19 infection in the previous 14 days. The screening form will include the following symptoms as having active COVID-19: fever, chills, cough, shortness of breath, difficulty breathing, lack of energy/general tired feeling, muscle or body aches, headache, new loss of taste or smell, sore throat/congestion/runny nose, nausea, vomiting, or diarrhea, abdominal pain, or skin rash.

2. Obtain consent and HIPAA authorization and allow an opportunity for questions.
3. Brief demographic questionnaire (race, ethnicity, sex, county of residence) and questions to assess intention to receive a COVID-19 vaccine.
4. Conduct interventions. All participants will have the opportunity to receive antibody testing using a finger stick (using the same methods as in the CATCH-UP Study, IRB #12582). After the antibody test is done and participants are waiting for the results (about 15 minutes), the participants will receive the interventions. If participants decline the antibody test, the interventions will begin once consent, HIPAA, and the brief demographic questionnaire are complete.
 - a. **Text message.** Participants will be randomized to either receive 1) a text message encouraging COVID-19 vaccination (treatment) or no text message (control). This factor will last less than 1 minute.
 - b. **Tailored messaging.** Participants will be randomized to receive 1) educational messaging about COVID-19 vaccines (treatment) or 2) an attention control educational message not related to COVID-19 (control). This will be delivered on a tablet through RedCap. This factor will last around 10 minutes.

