6. We will send participants a RedCap survey link through text message or email 30 days and 60 days after the intervention to assess intent to be vaccinated for COVID-19 and vaccine uptake, allowing time for both doses of the Pfizer and Moderna, single dose of Jansen’s COVID-19 vaccine, or boosters of vaccines to be delivered. We will also send up to three daily reminders to the participant to complete the common data elements survey if they did not complete it after the intervention.
7. For participants who agree, we will contact up to 60 participants to participate in an evaluation interview to help the personnel determine what did and did not work well during the intervention. This will be a 30 minute to one hour interview.

Aim 2.2. Full implementation.

Study Design. Participants will be randomized to a 2 x 2 x 2 fully crossed factorial design, creating 8 conditions to evaluate the contribution of each intervention component in an initial pilot/feasibility study. For each intervention site, we will collect a brief demographic survey through Research Electronic Data Capture (REDCap) software (Nashville, TN) to allow for descriptive statistics and ensure the randomization is balanced regarding these characteristics.

Intervention Procedure

All interactions with participants will occur through a tablet or through verbal communication.

1. Screening Form to identify eligibility for the study. This will include age, ability to read and speak English, vaccine status and dose information (see eligibility criteria), and having symptoms of COVID-19 or positive test for COVID-19 infection in the previous 14 days. The screening form will include the following symptoms as having active COVID-19: fever, chills, cough, shortness of breath, difficulty breathing, lack of energy/general tired feeling, muscle or body aches, headache, new loss of taste or smell, sore throat/congestion/runny nose, nausea, vomiting, or diarrhea, abdominal pain, or skin rash.
2. Obtain consent and HIPAA authorization and allow an opportunity for questions.
3. Brief demographic questionnaire (race, ethnicity, sex, county of residence) and questions to assess intention to receive a COVID-19 vaccine.

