 6. We will send participants a RedCap survey link through text message or email 30 days and 60 days after the intervention to assess intent to be vaccinated for COVID-19 and vaccine uptake, allowing time for both doses of the Pfizer and Moderna, single dose of Jansen's COVID-19 vaccine, or boosters of vaccines to be delivered. We will also send up to three daily reminders to the participant to complete the common data elements survey if they did not complete it after the intervention.
 7. For participants who agree, we will contact up to 60 participants to participate in an evaluation interview to help the personnel determine what did and did not work well during the intervention. This will be a 30 minute to one hour interview.

At all events, key personnel will also conduct a field observation of how the events flow, including external factors such as weather or logistical problems and where challenges to implementing the study or recruiting participants occurred. We will also conduct evaluation focus groups with event site staff to determine what did and did not work during the event.

We expect to recruit 2000 participants over the entire study period (Aim 2.1 and 2.2).

Factorial design. In a factorial research design, two or more independent variables are concurrently examined within the same trial. The three factors are crossed with one another to create a total of eight experimental conditions. An equal number of participants are randomly assigned to each condition, using a random number generator. This is not an 8-arm randomized controlled trial, but instead allows for an efficient examination of main effects for each variable in a sample of 2000 participants (including Aim 2.1 and Aim 2.2).

This approach allows examination of three key treatment development questions in a much more time-efficient and economical manner by simultaneously performing three studies within the single trial. This achieves power to detect between-group differences that is equivalent to performing three separate randomized trials. Investigators who are providing the intervention and conducting analysis will be not be masked to study assignment due to challenges in maintaining the masking in an educational intervention. For all sites, including Aims 2.1 and 2.2, we expect to recruit 2000 participants.

Identifiers might be removed and the de-identified information may be used for future research without additional informed consent from the subject.

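### The primary comparison leaves out prior vaccination and site; adjusting for them gains precision without extra recruitment, and the allocation method should be stated

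*Combined protocol and SAP*

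**What the plan says.** **Allocation.** The Factorial design paragraph of section D states: "An equal number of participants are randomly assigned to each condition, using a random number generator". No section names blocks, strata, minimisation, or when an allocation is released.

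**Balance.** Under Aim 2.2, Study Design, a REDCap demographic survey is collected "to allow for descriptive statistics and ensure the randomization is balanced regarding these characteristics". The pilot (Aim 2.1) makes the same claim for its survey: "assessment of study outcomes, and ensure the randomization is balanced regarding these characteristics". Section I, Aim 2 Analysis, describes only a later check: "We will compare the baseline characteristics to assess whether randomization distributed covariates evenly".

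**Outcome.** Section D measures the primary outcome with a first-vaccine item and, for people who have had one Janssen dose or two mRNA doses, a booster item: "how likely are you to get an approved booster shot". Section E admits both never-vaccinated and previously vaccinated adults.

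**What is known beforehand.** In the Aim 2.2 procedure, vaccine status and doses are taken on the screening form (step 1). Step 3 is: "Brief demographic questionnaire (race, ethnicity, sex, county of residence) and questions to assess intention to receive a COVID-19 vaccine". Randomisation and the interventions appear at step 4.

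**Test.** Section I assesses each component against intention measured immediately afterwards, and its sample size paragraph calls this a two-sample comparison. The tests named are chi-square for binary outcomes and t or Wilcoxon for continuous ones, with no stratum or covariate. A GEE is added for the longitudinal data, without model terms.

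**The concern.** The outcome pools two different questions, and series completion decides which one applies. People who never started or never finished the series probably answer differently from people considering a booster. An unadjusted test leaves that known difference in its error term, although the variable that explains it is already on the screening form. Site is treated the same way, even though the power paragraph assumes correlation within site.

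What is at stake is the precision of each main effect. There is also a prespecification point: a balance check with no stated consequence, made by analysts who are not masked, leaves open whether and how the result would lead to adjustment.

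Secondarily, the plan makes two promises about allocation (equal numbers, ensured balance) and states no mechanism that would deliver either.

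**Working it through.** **1. The plan's own figure.** Section I claims over 80% power for a mean difference of 20 with SD 5, alpha 0.05 (taken as two-sided), ICC 0.01 and 167 per site. That difference is 20/5 = 4 SDs. The usual formula gives 2 × (1.96 + 0.84)² / 4² = 0.98, that is, 1 per group. The design effect is 1 + 166 × 0.01 = 2.66; with or without it, power is 1.000 for any number of sites. The claim is true but does not show how much precision the trial needs. The plan gives no figure for balance or covariate gain.

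**2. Does unequal allocation matter?** Suppose allocation is simple.
- 2000 people over eight cells: cell SD = √(2000 × 1/8 × 7/8) = 14.8; the probability that all cells are equal is 2000!/(250!)⁸ × 8⁻²⁰⁰⁰ ≈ 2 × 10⁻¹¹.
- Main effects compare halves: SD = √(2000 × 1/4) = 22.4, so the 95% range of the split is 956 to 1044. A comparison with 80.0% power at 1000:1000 (50% v 56.25%) keeps 79.9% at 956:1044.
- The 2000 includes the pilot of about 500, in which motivational interviewing is not described as randomised. About 2000 − 500 = 1500 reach the eight conditions (187.5 per cell, SD 12.8; split 712 to 788).
- For a 50% covariate, the 95% chance difference between factor levels is 1.96 × √(0.25 × 2/1000) = 4.4 points at 2000, 5.1 at 1500, and about 15 within one 167-person site.

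These differences are random, so they do not bias the test.

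**3. Precision available from prior vaccination.** Let q be the proportion with the series not completed, d the difference in the rate of likely responses, and p the overall rate. On the risk-difference scale, the share of variance between strata is s = q(1 − q)d² / [p(1 − p)], and the participants-equivalent is N × s/(1 − s). The documents give none of q, d or p; all are assumed.

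| q | d | p | s | of 2000 | of 1500 |
|---|---|---|---|---|---|
| 0.2 | 0.2 | 0.5 | 0.0064/0.25 = 0.026 | 53 | 39 |
| 0.5 | 0.2 | 0.5 | 0.0100/0.25 = 0.040 | 83 | 63 |
| 0.2 | 0.4 | 0.5 | 0.0256/0.25 = 0.102 | 228 | 171 |
| 0.5 | 0.4 | 0.5 | 0.0400/0.25 = 0.160 | 381 | 286 |
| 0.5 | 0.4 | 0.3 | 0.0400/0.21 = 0.190 | 471 | 353 |

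For given q and d, p = 0.5 gives the smallest share, so the first four rows are lower limits. The 1500 column applies to motivational interviewing.

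**4. Site.** With the plan's ICC of 0.01, the gain is 2000 × 0.01/0.99 ≈ 20 participants.

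**5. Baseline intention.** An assumed correlation of 0.3 to 0.5 with the outcome leaves 1 − 0.09 = 0.91 to 1 − 0.25 = 0.75 of the variance. This is worth 2000/0.91 − 2000 ≈ 198 to 2000/0.75 − 2000 ≈ 667 participants.

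**6. Adjustment or allocation?** In a simulation of 2000 people in two groups with 35% not completed, the effective sample size after adjustment was 1998 with simple and 2000 with blocked allocation. With 12 sites (2000/167) crossed with vaccination it was 1976 v 2000. Blocking therefore adds about 2 to 24 participants, and the gain in step 3 comes from adjustment.

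**7. If strata are used to allocate but left out of the test.** For assumed strata R² = 0.09, the effective critical value is 1.96/√0.91 = 2.05. True type I error falls to 0.040, and power falls from 80% to 77.2%.

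**The case against.** A reader might infer that the generator is unrestricted, so that the plan cannot deliver what it promises. The documents do not say so. A random number generator can also produce a blocked list, and a sentence requiring equal numbers is consistent with one. What can be shown is that the method is unspecified. *Ensure* may also have been meant as *check*.

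A reader might also infer that chance imbalance invalidates the comparison, or that stratified randomisation is the remedy. Steps 2 and 6 do not support either. At this size, simple randomisation with a prespecified adjustment is a legitimate design. Restricted allocation also has costs here: sites are public events identified as they are scheduled, and staff are unmasked, so small site-by-vaccination strata would make block ends easier to guess.

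Three further points stand:
- Prior vaccination is not shown to be the strongest covariate; baseline intention may do more (step 5).
- Site is not wholly ignored, since the power paragraph uses an ICC and the GEE may account for site. Its gain of about 20 is small. With simple allocation and full crossing of 12 sites with vaccination, the loss of about 24 in step 6 would use it up.
- That analysts would adjust selectively after the balance check is a possibility; the plan proposes no such step.

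None of this defends leaving a known determinant of the outcome item out of the primary test.

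**Conclusion.** The concern holds as a matter of precision and specification. The primary two-group tests, as stated, omit prior vaccination, which determines which item supplies the outcome and is recorded before the interventions. Adjusting for it is worth from about 3% to 16% or more of outcome variance, roughly 50 to 380 or more of 2000 participants. That range is illustrative: it rests on assumed proportions and response rates, and on a binary outcome analysed on the risk-difference scale. Site adds little at the stated ICC, but it belongs in the model if allocation is restricted by site.

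The unadjusted main-effect tests remain valid, and unequal cells cost them almost no power. The unstated allocation method and the claim that a survey ensures balance are secondary points to clarify.

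**What to change.** **Analysis (section I).** Replace the two-group tests as the primary analysis with wording such as: *Post-intervention intention will be regressed on the randomised factors, adjusting for primary series completed or not (from the screening form) and site. For a binary outcome, adjusted risk differences will be reported. The motivational-interviewing effect will be estimated from Aim 2.2 participants.* A stratified test on the same variables would also serve. Use series completed or not, because the booster item follows that split; never v ever vaccinated would misplace people with one mRNA dose. Enter site as additive terms, define it (event or community), and state a rule for pooling small sites. Decide now whether baseline intention from step 3 is added. Keep the unadjusted tests as supportive.

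**Allocation (section D).** State how equal numbers are achieved, for example mixed permuted blocks within site, released only after step 3, and carry any allocation strata into the model. Blocks give near-equal, not exactly equal, counts: with site-stratified blocks of 8 over 12 sites, the simulated median gap between largest and smallest cell is 3, against 44 for simple allocation of 2000. State that about 1500 participants are allocated to the eight conditions.

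**Balance wording.** In Aims 2.1 and 2.2, replace *ensure* with *describe*, and present the baseline comparison as descriptive.

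**Cost.** A few lines of text. Prior vaccination and baseline intention are already collected, and no recruitment changes. Blocking, if chosen, needs an allocation table and carries some predictability, which mixed block sizes limit.
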